## 10.2 Subject Consent

### 10.2.1 Consent Materials

Geography-specific templates of the Patient Information and Informed Consent Form (PI/ICF) are available separate from this CIP. These templates may be modified to suit the requirements of the individual site. For US sites, this must include Health Insurance Portability and Accountability Act (HIPAA) Authorization language. This language may be incorporated into the ICF or (if required by the Ethics Board) included as a separate document.

Medtronic, Ethics Boards, and Competent Authorities (CA), where applicable, shall approve all informed consent documents prior to implementation in the study. Medtronic, Ethics Boards, and CAs, where applicable must pre-approve all language changes to the PI/ICF throughout the course of the study prior to implementation; this includes initial submission, annual reviews (if applicable), and protocol amendment reviews. The original Ethics Board-approved PI/ICF must be retained at the investigational site.

Any revisions required by the Ethics Board must be forwarded to Medtronic for review and approval before the revised consent form is returned to the Ethics Board for final review and full approval.

Medtronic will provide any important new information that impacts the health, safety or welfare of study subjects, for inclusion in PI/ICF updates as it becomes available. Sites should follow any Medtronic, CA, or Ethics Board requirements for disseminating new information and re-consenting subjects during the course of the study.

### 10.2.2 Informed Consent Process

The investigator (or authorized designee) was required to administer the approved PI/ICF to each prospective study patient without coercion or undue improper influence on, or inducement of, the patient to participate. During the consent discussion the investigator (or authorized designee) was required to fully inform the patient of all pertinent aspects of the study, using native non-technical language that was understandable to the patient. The patient was required to be informed about their right to withdraw from the study at any time and for any reason without sanction, penalty, or loss of benefits to which the patient was otherwise entitled, and also be informed that withdrawal from the study would not jeopardize their future medical care. The patient was required to also be informed that by participating in the study, they were not waiving their legal rights. The patient was required to have ample time and opportunity to inquire about details of the study, and to decide whether or not to participate in the clinical study. All questions about the study were to be answered to the satisfaction of the patient. All items discussed in the PI/ICF was required to be explained.

Informed consent was to be obtained in writing from the patient. The date of consent and process by which the consent was obtained (including documentation of special circumstances, if applicable) was to be documented in the patient's medical record prior to any study-specific procedures. Patient informed consent was required to be obtained in accordance with the national and local laws, regulations and guidelines of each site. The institutional standard procedure consent form does not replace the study PI/ICF.

The subject's signature and date of consent serve to document that they understood the written and verbal information that the investigator (or authorized designee) provided, and their agreement to participate and collect their medical data. The investigator (or authorized designee) who conducted the informed consent process was required to provide their handwritten signature and date the consent was completed on the ICF. The ICF was required to be signed and dated prior to any specific protocol assessments or procedures.

However, if any required baseline exams (e.g. IVUS, venography, Duplex Ultrasound, blood labs) had been performed as standard of care prior to consenting the subject, they could have been used as the baseline/qualifying exams (and were not considered a deviation), provided they met the following criteria:

- the investigator determined that the exams contained the protocol-required data and were adequate for evaluation;
- the exams were completed within 30 days prior to the scheduled implant procedure.

The original signed and dated ICF is kept at the investigational site. A copy of the signed and dated ICF was to be provided to the subject.

### 10.2.3 Special Circumstances for Informed Consent Process and Signature

If a patient could not read or write, an impartial witness was required to be present during the entire informed consent discussion. The written PI/ICF (and any other information) could be read aloud and explained to the patient and witness. The witness would then sign and personally date the ICF attesting that the information was accurately explained and that consent was freely given. The patient would sign and date if possible.

Given the investigational status of the Abre system in the US at the time of enrollment, and the availability of approved endovenous stents in some geographies, emergency cases were not allowed under this protocol.

Given the commercial availability of other endovenous stents in some geographies, requests for compassionate use of the Abre stent were not anticipated.

## 10.3 Screening/Baseline Procedures (-30 days)

The following baseline evaluations were completed and recorded on the appropriate eCRF. Baseline evaluations were to be completed within 30 days of the scheduled implant procedure unless otherwise specified.

- Informed consent
- Demographics
- Medical history
- Physical examination
- Pregnancy test for women of child bearing potential only. This must be done within 7 days prior to the index procedure.
- CEAP classification (for both limbs)
- Physical assessment of limbs
- Villalta score, VCSS (for both limbs)
- Quality of life questionnaires: EQ-5D and VEINES-QOL/Sym
- Blood tests (See **Section 10.3.2 Blood Tests**)
- INR required for subjects on warfarin
- Venogram or IVUS for diagnosis if performed as standard of care. This diagnosis can also be made during the index procedure, prior to stenting.
- Duplex ultrasound (DUS) (both limbs)
- Medications: Antithrombotics, Antibiotics, Immunosuppressants, NSAIDs, Steroids, Diuretics, Calcium-channel blockers

- Adverse event assessment need to be done as of the moment the subject is enrolled in the study (i.e. subject signed and dated the informed consent form).

### 10.3.1 Demographics, Medical History & Physical Examination

A careful medical history and physical examination were to be taken prior to the implant procedure. For any interventions, the date of the most recent intervention was to be captured.

Data collected at baseline:

- Gender
- Age at time of enrollment
- Race/Ethnicity, to be collected per the FDA Guidance for Collection of Race and Ethnicity Data in Clinical Trials (2016), in support of regulatory submissions in the US (FDA).
- Risk factors, such as hypertension, diabetes, hyperlipidemia, tobacco use, obesity (BMI), previous knee/hip replacement, immobility and any other cardiovascular risk factors, with measure of severity and current treatment
- Co-existing cardiovascular conditions (including, but not limited to superficial ablation, congestive heart failure, peripheral vascular disease, previous myocardial infarction (MI))
- Symptoms
- Physical examination
- Assessment of target lesion and access vessel characteristics
- Medications: Antithrombotics, Antibiotics, Immunosuppressants, NSAIDs, Steroids, Diuretics, Calcium-channel blockers, Statins;

### 10.3.2 Blood Tests

The following blood tests were required:

- Serum creatinine for GFR calculation (GFR must be  $\geq 30$  to be included in the study). Any method to perform the GFR calculation is allowed;
- White Blood Cell (WBC) count (must be  $\geq 3,000$  cells/mm $^3$  and  $\leq 12,500$  cells/mm $^3$  to be included in the study)
- Platelet count (must be  $\geq 50,000$  cells/mm $^3$  and  $\leq 1,000,000$  cells/mm $^3$  to be included in the study);
- Hemoglobin;
- Hematocrit;
- INR required for subjects on warfarin.

## 10.4 Acute DVT Subjects

Acute DVT subjects were required to be treated with the Abre stent within 14 days after onset of symptoms. Subjects with acute deep vein thrombosis (DVT) were required to first undergo successful treatment of acute thrombus. This was required to be done within 14 days after the onset of symptoms and only with market released devices. Successful treatment was defined as less than 30% residual thrombus by venogram, as determined by physician, and no bleeding, no symptomatic pulmonary embolism (confirmed by imaging), and no renal compromise. Subjects with underlying obstructive lesions were then permitted to be included in the study within the same procedure, or the procedure may have been staged.

## 10.5 Implant Procedure

Detailed information on intended use of the device, indications, and contraindications, as well as a complete list of warnings, precautions, and potential adverse events, were included in the IFU. The IFU was provided with each device.

### 10.5.1 Procedure Data

The following data was to be recorded for each subject in the study:

- Date of procedure
- Indication for stenting: acute DVT, NIVL, PTS, and any combination of these
- Identification data for the stent(s)
- Details of procedure, including any adjunctive vascular procedure performed
- Chosen access sites
- Medications: Antithrombotics, Thrombolytics
- Assessment of handling, visualization, deployment, and withdrawal
- Assessment of patency, positioning, and integrity of the stent
- Adverse events
- Comparison of intended and actual stent location
- Date of hospital discharge

### 10.5.2 Imaging

During the index procedure, venography and IVUS were required, prior and post stent placement to aid with stent sizing and lesion assessment.

### 10.5.3 IVC Filter Placement

Inferior Vena Cava (IVC) filter placement was at the discretion of the physician. IVC filter placement was not encouraged, however may have been considered in the following situations:

- presence of floating thrombus in ilio caval segments;
- planned use of mechanical thrombectomy in the presence of acute thrombus.

IVC filter was recommended to be removed as soon as deemed safe by the operating physician.

[figure not shown]
### 10.5.4 Inflow Requirements

Negative outcomes are best avoided by good inflow directed by IVUS in the least diseased portion of the vein above the deep femoral vein. Good inflow involves either the femoral or deep femoral vein inflow being patent and at least a caudal section of the common femoral vein that is free of significant disease. Good inflow was to be determined by the investigator.

### 10.5.5 Lesion(s)

The target lesion was defined as non-malignant venous obstruction within the common iliac, external iliac, and/or common femoral vein: the proximal point of the obstruction may have extended to the iliac venous confluence of the inferior vena cava and the distal point may have been at or above the deep femoral vein.

When stented, the complete stented area was considered 'lesion' and was to be treated as such during follow-up assessments.

**Figure 5. Venous anatomy**

## 10.5.6 Predilation

Access site was to be at the discretion of the physician, however it was strongly recommended not to use the ipsilateral common femoral vein and access from the ankle.

Predilation of the lesion with a balloon catheter was required to be the same diameter of the stent to be implanted, i.e. if a 14 mm stent was to be implanted, a 14 mm diameter balloon was required to be used. A high pressure balloon was highly recommended.

At a minimum the balloon should have been inflated up to nominal pressure and should have been inflated within the segment that was intended to be stented. The balloon would then have been removed from the subject while access with the guidewire was maintained.

## 10.5.7 Stent Size Selection

To optimize visualizing of the true extent of a venous lesion, venogram and IVUS could have been used. However, IVUS was the preferred modality.

### **Stent length**

It is important that the proximal and distal ends of the stents lie in a relatively normal/healthy venous segment. Therefore, a stent length must have been chosen that extended cranial and caudal to the target lesion, covering at minimum 1 cm cranial and 1 cm caudal, if the disease allowed. Additional coverage can reduce the risk of restenosis. The Abre stent should not have occluded the inflow of the contralateral limb or touch the contralateral wall.

### **Stent diameter**

Vein diameters could be measured using one of the following two methods:

1. Using IVUS: take the average of the minimum and maximum diameters of a normal segment of vein in the same anatomical segment;
2. Using Venogram: take the average diameter of a normal segment of vein in the same anatomical segment in two planes.

Considering the estimated anatomic vessel diameter, the appropriate Abre stent diameter was to be selected. A stent with a diameter of at least 2 mm more than the chosen reference vessel diameter was recommended to achieve good wall apposition.

Reference vessel diameter could have been obtained by one of the following methods:

1. Measure the diameter of a normal segment of an appropriate segment of the target vein (which generally should be the most caudal segment);
2. Measure the diameter of the vein in an appropriate segment of the contralateral limb;
3. Use the literature reference vessel diameter for the appropriate segment:
  - a. Common Iliac Vein: 16 mm
  - b. External Iliac Vein: 14 mm
  - c. Common Femoral Vein: 12 mm

Proper size selection reduces stent migration and ensures appropriate stent apposition to the vessel wall.

## 10.5.8 Stent Placement

The Abre delivery system should have been advanced until the leading edge of the stent is beyond the target lesion. Whenever possible, one stent should have been used to cover the entire length of the target lesion.

### Multiple stents

If multiple stents were needed to cover the entire length of the target lesion, they should have been implanted in an overlapping manner with a minimum overlap of 1.5 cm. The more cranial stent should have been placed first. It was recommended to use the same stent diameter. If different diameters were needed, the smaller diameter stent should have been placed first. Non-stented areas in between stents, i.e. skip areas, were not allowed. Stents ending in the inguinal ligament were to be avoided.

## 10.5.9 Post-dilation

Post-dilation of the lesion with a balloon catheter was recommended up to the diameter of the implanted stent to achieve the expected nominal stent diameter.

## 10.6 Hospital Discharge

The discharge visit occurred at the time of subject's discharge from the hospital. The following evaluations were completed and data was recorded on the Discharge eCRF:

- Duplex ultrasound (target limb). The DUS examination immediately after the index procedure needs to be performed between 0 and 7 calendar days from the index procedure. When the first examination after the procedure is non-diagnostic, a second exam has to be performed as soon as possible. Every effort should be made to perform this within 7 calendar days after the index procedure;
- Duplex ultrasound (contralateral limb); image of the CFV waveform only.
- Physical assessment of limbs;
- Adverse events/device deficiency;
- Medications: Antithrombotics, Antibiotics, Immunosuppressants, NSAIDs, Steroids, Diuretics, Calcium-channel blockers, Statins;
- Compression stockings. Subjects will be instructed to wear medical grade ( $\geq 20$  mm Hg) compression stockings (above or below knee) as instructed by their physician with compliance encouraged. The use of compression stockings will be evaluated via the VCSS;
- Discontinuation information (in case the subject ends involvement in the study).

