## Appendix E Venous Clinical Severity Score (VCSS)

Venous disease severity measurement intended to evaluate the responses to changes in disease severity over time and in response to treatment.

	None: 0	Mild: 1	Moderate: 2	Severe: 3
Pain or other discomfort (i.e. aching, heaviness, fatigue, soreness, burning)  Presumes venous origin		Occasional pain or other discomfort (i.e. not restricting regular daily activities)	Daily pain or other discomfort (i.e. interfering with but not preventing regular daily activities)	Daily pain or discomfort (i.e., limits most regular daily activities)
Varicose Veins “Varicose” veins must be $\geq 3$ mm in diameter to qualify in the standing position		Few: scattered (i.e., isolated branch varicosities or clusters) Also includes corona phlebectatica (ankle flare)	Confined to calf or thigh	Involves calf and thigh
Venous Edema Presumes venous origin		Limited to foot and ankle area	Extends above ankle but below knee	Extends to knee and above
Skin Pigmentation Presumes venous origin  Does not include focal pigmentation over varicose veins or pigmentation due to other chronic diseases (i.e., vasculitis purpura)	None or focal	Limited to perimalleolar area	Diffuse over lower third of calf	Wider distribution above lower third of calf
Inflammation More than just recent pigmentation (i.e., erythema, cellulitis, venous eczema, dermatitis)		Limited to perimalleolar area	Diffuse over lower third of calf	Wider distribution above lower third of calf
Induration Presumes venous origin of secondary skin and subcutaneous changes (i.e., chronic edema with fibrosis, hypodermatitis)  Includes white atrophy and lipodermatosclerosis		Limited to perimalleolar area	Diffuse over lower third of calf	Wider distribution above lower third of calf

Active Ulcer Number	0	1	2	≥3
Active Ulcer Duration (longest active)	N/A	<3 mo	>3 mo but <1 y	Not healed for >1 y
Active Ulcer Size (largest active)	N/A	Diameter <2 cm	Diameter 2-6 cm	Diameter >6 cm
Use of Compression Therapy	0 Not used	1 Intermittent use of stockings	2 Wears stockings most days	3 Full compliance: stockings

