### 7.9.3 Secondary Endpoints

To assess how the subjects are doing clinically, the following secondary endpoints will be evaluated. All secondary endpoints will be evaluated using descriptive statistics. No inferential analyses are planned. Detailed analysis methods for core laboratory endpoints and endpoints assessed by office visits can be found in Section 10.

In addition, time-to-event analysis will be performed and Kaplan Meier (KM) estimates with two-sided 95% confidence interval using Peto formula will be reported for major adverse events (MAE) and its component events through 12 months, and annually through 36 months.

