- 11. Change in VILLALTA Score at 6-, 12-,24-, and 36 months:** Defined as the change in VILLALTA score at 6, 12, 24, and 36 months compared to baseline.
- 12. Change in EQ5D Quality of life Score at 6-, 12-, 24-, and 36 months:** Defined as the change in Quality of Life Score as assessed by EQ5D questionnaire at 6, 12, 24, and 36 months compared to baseline.

- 13. Change in VCSS Score at 6-, 12-, 24-, and 36 months:** Defined as the change in VCSS Score at 6, 12, 24, and 36 months compared to baseline.
- 14. Major bleeding complication at 30 days, 6-, 12-, 24- and 36 months:** A blood loss leading to transfusion of whole blood or red cells provided hemoglobin drop of 3 g/dL (1.86 mmol/L) or more is related to bleeding occurring during the index procedure through 36 months post-index procedure.
- 15. Medical resource utilization through 36 months** including length of stay and re-hospitalizations.

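### The change in total VCSS carries change in stocking use as well as change in disease, because stocking use is one of the ten items and subjects are told after baseline to wear stockings

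*Protocol*

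**What the plan says.** Protocol 10.3 places the first VCSS before the procedure: "Villalta score, VCSS (for both limbs". At discharge, Protocol 10.6 adds an instruction: "Subjects will be instructed to wear medical grade" stockings, "as instructed by their physician with compliance encouraged". It names the tool that records whether this is followed: "The use of compression stockings will be evaluated via the VCSS".

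Protocol Appendix E gives the scale. Nine items cover pain, varicose veins, edema, pigmentation, inflammation, induration, and ulcer number, duration and size. The tenth is compression use, running from 0 for none to 3, which is labelled "Full compliance: stockings". Appendix E describes the instrument as a "Venous disease severity measurement intended to evaluate the responses to changes in disease severity over time and in response to treatment".

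The endpoint is item 14 in Protocol 6.3.2 and item 13 in SAP 7.9.3: "Defined as the change in VCSS Score at 6, 12, 24, and 36 months compared to baseline". SAP 7.11 repeats it. Neither document plans item-level reporting, a score without the compression item, or an adjustment for stocking use. SAP 7.9.3 sets the status of the endpoint: "All secondary endpoints will be evaluated using descriptive statistics. No inferential analyses are planned".

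**The concern.** One instrument does two jobs here. It is the measure of clinical change after stenting, and it is also the record of whether subjects wear the stockings they were told to wear. On this scale, following the instruction counts as a worse score.

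The instruction comes after the baseline assessment, so any resulting change in wear falls inside the before-after difference. A control group given the same instruction would let the shift cancel. This study has a single arm, so nothing removes it.

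What is at stake is how a secondary clinical endpoint is read at 6, 12, 24 and 36 months. From the total alone, a reader cannot separate a change in symptoms and signs from a change in stocking habit. Nor can the reader tell whether movement between visits comes from one or the other.

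**Working it through.** **Inputs**
- Number of VCSS items: 10, each scored 0-3 (count of the rows in Protocol Appendix E).
- Compression item: 1 of the 10, scored 0-3, higher with more use (Protocol Appendix E).
- Literature VCSS: 9.7 before and 3.7 after intervention (Protocol Appendix A, Table XIV). This is the only VCSS magnitude in the documents.
- Stocking use at baseline or at any follow-up visit: not given in either document.

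**The documents' own figure.** 9.7 − 3.7 = 6.0, which matches the change printed in Table XIV.

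**Weight of the item.** The full scale is 10 × 3 = 30 points. The compression item is 3/30 = 10% of it. The other nine items hold 9 × 3 = 27 points, or 90%.

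**How the item enters the change.** Define improvement as baseline minus follow-up. Let I9 be the mean improvement in the nine other items and s the mean rise in the compression item from baseline. Then

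improvement in total VCSS = I9 − s.

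For one subject s lies between −3 and +3. For the group, if the mean item score at baseline is c0, s lies between −c0 and 3 − c0. A group mean of +3 would need every subject to go from no use to full use. Subjects who already wear stockings at baseline have less room to rise.

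**Illustration.** Take I9 = 6.0, borrowing the size of the literature change, and assume values for s:

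| Assumed mean shift in item | If use rises: 6.0 − shift | If use falls: 6.0 + shift |
|---|---|---|
| 0.5 | 5.5 | 6.5 |
| 1.0 | 5.0 | 7.0 |
| 1.5 | 4.5 | 7.5 |

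With no change in use, s = 0 and the total is undisturbed.

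**Between visits.** The same identity holds from one follow-up visit to the next. If mean wear fell by some amount between two visits, the total would improve by that amount with the nine items unchanged, even while wear stayed above its baseline level. Whether wear rises, falls or stays level is not stated.

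**The case against.** Several points against this have force.

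- **Most of the score is disease.** Nine of ten items, 27 of 30 points, describe symptoms, signs or ulcers. A reader might infer that the score follows stocking compliance instead of disease. Appendix E does not support that, and the point is limited to stocking use entering alongside disease.
- **The size is unknown.** A reader might suppose that half the subjects go from no stockings to full use, giving 0.5 × 3 = 1.5 points. Nothing in the documents supports that rate. Protocol 5.1 says patients with postthrombotic symptoms are often managed with compression hose, and SAP 6.4 allows up to 49% of included subjects (98) in that category. Many may therefore already score above zero at baseline. The instruction is also left to the physician.
- **Declining wear is not documented.** A reader might expect use to fade between 6 and 36 months and flatter the later visits. It might, but no section says so.
- **The 6.0 is only a yardstick.** It comes from the nine series that reported a post-intervention VCSS. Appendix A does not say whether their scores included the compression item. If they did, 6.0 already contains whatever stocking effect those series had, so a hypothetical shift divided by 6.0 does not measure lost stent effect.
- **Other measures cover the ground.** Villalta, VEINES-QOL/Sym and EQ-5D are reported at the same visits and have no compression item.
- **The instrument is used whole.** Change in its total is a legitimate endpoint, and a nine-item score is not the published total.

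All of this limits the size and reach of the point. It leaves the structure standing: the item is in the total, the instruction follows baseline, there is no control group, and no planned table separates the two. Protocol 10.6 does suggest that someone intends to look at the item, but the SAP specifies no output for it.

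**Conclusion.** The change in total VCSS mixes change in stocking use with change in disease. The effect on one subject is at most 3 points in either direction. Improvement is understated if use rises from baseline and overstated if use falls below baseline.

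The mean effect cannot be calculated from the documents. The illustrative 5.5 to 4.5 rests on two assumptions: a nine-item improvement of 6.0 and a mean rise in the item of 0.5 to 1.5. A fall of the same size gives 6.5 to 7.5.

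The consequence is modest. The endpoint is descriptive, and study success under Protocol 14.5 depends only on the two primary endpoints. Alpha, power and the performance goals are untouched. If use rises after discharge, the distortion runs against the device, so in that case it would not create an apparent benefit. This is a reporting improvement and does not count as a flaw in the study's main conclusions.

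**What to change.** In SAP 7.9.3 item 13 and SAP 7.11:

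1. Keep the change in full VCSS (0-30) as planned.
2. Beside it, report the change in the nine-item score without the compression item (0-27) at 6, 12, 24 and 36 months.
3. Tabulate the compression item by visit, including baseline, so that the direction and size of any shift can be seen.
4. Label the nine-item analysis as post hoc for any visit already analysed when it is added. The Protocol Synopsis says the 12-month data had been collected for the premarket application, so this is likely to apply to the 6- and 12-month results.

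The cost is about one extra table, from data the VCSS form already requires. The nine-item score is non-standard, so it should stand beside the published total and not replace it. No change to the stocking instruction is implied.
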